Laboratory- confirmed influenza illness rates in HCP receiving AD	Clinical	Comparison of persons who did and did not become sick with influenza after receiving the AD or SD	Person became sick with influenza after receiving AD or SD vaccine Person did not become	Nasal swab specimen tests positive for influenza by PCR	Quantitative Discrete	PCR assay (laboratory)
vaccine		vaccine	sick with influenza after receiving AD or SD vaccine	Nasal swab specimen tests negative for influenza by PCR		

Secondary Objective 6: To assess the adverse events among HCP receiving SD and AD influenza vaccines

				Criterios de	Tipo de	Instrumento de
Variable	Dimensión	Indicador	Valores	medición	variable/indicador	medición
	(Dimension)	(Indicator)	(Values)	(Measurement criteria)	(Type of variable/indicator)	(Measurement instrument)
Adverse events in HCP receiving AD vs. SD vaccine	Anticipated (Clinical)	Local reactions: pain on vaccination site, swelling, lump itching, bruising	Yes	Person had a local and/or systemic reaction(s) after receiving AD or SD vaccine	Quantitative Discrete	Post-vaccination surveillance via follow-up visits and monitoring (calls, surveys)

	AND/OR Systemic reactions: fever (≥38°C), muscle ache, joint pain, headache, malaise, fatigue, weakness, sweating, shivering	No	Person did not have a local and/or systemic reaction(s) after receiving AD or SD vaccine		
	Death, life- threatening adverse event, hospitalization or prolongation of existing	Yes	Person had a serious adverse event after receiving the AD or SD vaccine		Post-vaccination surveillance via
Serious, Unanticipated (Clinical)	hospitalization, a persistent or significant incapacity affecting normal life activities, and other unanticipated event that seriously impacts the health of participants	No	Person did not have a serious adverse event after receiving the AD or SD vaccine	Quantitative Discrete	follow-up visits, monitoring (calls, surveys), and hospitalizations

Below we describe the statistical tests that we will perform to address each primary and secondary objective, highlighting which study population will be included for each analysis. All statistical tests will be performed with a significance level of 5% and a statistical power of 80%.

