5) To evaluate laboratory-confirmed influenza illness rates in the group receiving AD influenza vaccination compared to the group receiving SD influenza vaccination. Using data collected through active surveillance, we will calculate incidence densities and use descriptive statistics and Z-test to assess differences in the proportion of HCPs who had laboratory-confirmed influenza (as determined by PCR on nasal swab samples) during the period of the clinical trial among the HCP who received the influenza vaccines AD vs. SD. A Cox regression model will be used to adjust the risk of developing influenza between both groups according to demographic and occupational characteristics. Health personnel participating in the clinical trial will be included as a study population for these analyzes.

6) To assess the adverse events among HCP receiving SD and AD influenza vaccines. Using data collected through active surveillance, we will use descriptive statistics and the Z test to assess the differences in the proportions of adverse events (anticipated and serious) between the HCP who received the AD and SD

influenza vaccines. All health personnel participating in the clinical trial will be included as a study population for these analyzes.

Table 1: Summary of Analysis by Endpoints and Analysis Populations.

OBJECTIVE	VALUATION CRITERIA	STATISTICAL TEST	POPULATION OF ANALYSIS
Primary Efficacy Analysis			
To determine if the AD influenza vaccine generates superior immunogenicity than the vaccine against SD influence without adjuvant among the HCP.	Immunogenicity - superior serumconversion of AD vaccine versus SD vaccine in HCP.	Wilcoxon signed rank test.	PP population
Secondary Efficacy Analysis			
To compare the post-vaccine immune response, in approximately 28 days after vaccination and at the end of the influenza season, among the HCP with a history of influenza infection confirmed by PCR result during any of the 6 years during the previous cohort study (2016 to 2021).	Post-vaccination immune responses, approximately 28 days after vaccination and at the end of the season, among HCPs with a history of PCR-confirmed influenza infection	Wilcoxon signed rank test.	ITTm1

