To compare the post-vaccine immune response, in approximately 28 days after vaccination and at the end of the influenza season, among the HCP who did not have a history of influenza infection confirmed by PCR result during any of the 6 years during the previous cohort study (2016 to 2021); among those with information available during the 6- year cohort.	Post-vaccination immune responses, at approximately 28 days after vaccination and at the end of the season, among HCPs with no history of PCR- confirmed influenza infection.	Wilcoxon signed rank test.	ITTm2
Examine whether the number of prior vaccinations against influenza during the previous 10 years, as documented in the medical records, modifies the immune response after receiving the AD or SD vaccine in approximately 28 days after vaccination and at the end of flu season.	Immune responses after receiving the AD or SD influenza vaccine, approximately 28 days after vaccination and at the end of the season	Descriptive statistics: multivariable logistic regression model	ITTm
Analyze and identify risk factors for a suboptimal response (lack of seroconversion / sero protection) to standard dose (SD) and / or adjuvanted (AD) influenza vaccines	Risk factors for suboptimal response (lack of seroconversion / seroprotection)	Descriptive statistics. Generalized linear models (GLM) with Poisson or binomial functions as appropriate	ITTm

To assess rates of laboratory-confirmed influenza illness in the group that received the AD adjuvanted influenza vaccine compared to the group that received the standard dose SD influenza vaccine.	Laboratory confirmed influenza illness rates among HCP receiving influenza vaccines AD vs. SD	Descriptive statistics., Calculation of incidence densities. Multivariate Cox Regression Model.	ITTm
Security Analysis			
To assess adverse events among HCP who received SD and	Frequency of AE	Descriptive statistics and	Security
AD influenza vaccines		Z test to evaluate	Population
		differences in	
		proportions	

- Population by Protocol: All HCPs vaccinated with any of the research products.
- ITTm population: HCPs who, having been vaccinated, became ill and did not become ill with influenza after receiving the AD or SD vaccine.
- ITTm1 population: HCPs may, having been vaccinated, became ill with influenza after receiving the AD or SD vaccine at approximately 28 days after vaccination and at the end of the season.

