13.1.2. Definition of a SAE

If an event is not an EA as defined above, then it cannot be an EAS, even if the seriousness conditions are met.

An SAE is defined as any detrimental medical event that, at any dose:

- Causes death.
- Is life threatening: The term "life threatening" in the definition of "serious" refers to an event in which a subject was at risk of dying at the time the event occurred. It does not refer to an event that hypothetically could have led to death if it had been more serious.
- Requires hospitalization or the extension of an existing hospitalization. In general, hospitalization means that the subject stayed (usually involving a stay of at least one night) in the hospital or emergency room for observation and / or for treatment that would not have been adequate in the doctor's office or in an outpatient setting. Complications that occur during hospitalization are EA. If a complication prolongs hospitalization or meets any other criteria for seriousness, it will be considered serious. If there are doubts as to whether there was a "hospitalization" or if it was necessary, the AE should be considered serious.

Hospitalization for scheduled treatment of a pre-existing condition that did not get worse from the start is not considered an AE.

• Causes a persistent disability / incapacity: The term disability means a significant impairment in a person's ability to perform normal life activities.

This definition does not seek to include experiences of relatively minor medical relevance, such as uncomplicated headache, nausea, vomiting, diarrhea, flu, and accidental trauma (for example, sprained ankle) that could hinder or prevent daily activities. , but not a significant disorder.

- It is a congenital anomaly / It is a congenital anomaly / congenital malformation in the subject's offspring.
- It is a significant medical event: Medical or scientific judgment should be used when deciding whether a SAE report is appropriate in other situations, such as major medical events that may not pose an immediate risk to life or result in death or hospitalization, but which may endanger the subject or may require medical or surgical intervention to avoid one of the other outcomes described in the definition above. In general, these events should be considered serious.

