13.1.4. AE and / or SAE registration

The investigator is responsible for recording all AEs / SAEs observed during the trial, that is, from the moment the subject gives informed consent until the end of the trial visit or until the last follow-up visit.

When an AE / SAE occurs, it is the investigator's responsibility to review all documentation (eg, hospital progress notes, laboratory reports, and diagnostic reports) related to the event.

The researcher must then record the information of all relevant AE / SAE in the eCRF.

SAE must be reported to the sponsor within 24 hours.

It is not acceptable for the investigator to send photocopies of the subject's medical records to the sponsor instead of completing the AE / SAE screen in the eCRF.

There may be instances in which copies of medical records for certain cases are requested by the sponsor. In this case, all the identification data of the subject, with the exception of the subject number, will be deleted in the copies of the medical records before they are sent.

The investigator should try to establish a diagnosis of the event based on the signs, symptoms, and / or other clinical information. Whenever possible, the diagnosis (not individual signs / symptoms) will be documented as AE / SAE.

The investigator should document and medically evaluate Adverse Events of Special Interest (AESIs) and overdose cases, and the result should be described on the SAE / AESI / overdose / misuse report form.

The investigator should document and medically evaluate the pregnancies, and the outcome should be described in the pregnancy notification form to be sent to the sponsor.

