13.1.8. Reports of other events

A. *Pregnancy reporting and monitoring*: Pregnancy is an exclusion criterion for enrollment in this trial, but participants could become pregnant during their active participation in this trial.

Any pregnancy in a participant who has received a study vaccine must be reported to the sponsor within 24 hours of the time the center becomes aware of its incidence through a pregnancy report form. If the participant becomes pregnant during the trial, she will not receive any additional doses of any study vaccine provided by the sponsor. The pregnancy should be followed to determine the outcome, including spontaneous or voluntary termination, details of the birth, and the presence or absence of congenital malformations, congenital anomalies, or maternal and / or newborn complications. This follow-up should be done even if the expected duration of the safety follow-up for the trial has ended.

The trial site should keep in contact with pregnant participants to obtain information on the outcome of the pregnancy.

Any complication during pregnancy (eg, gestational diabetes or eclampsia) should be considered an AE; however, these complications could result in the event being considered an SAE. Miscarriages, stillbirth, stillbirth, and reported birth defects in the baby are always considered SAE. The pregnancy itself will not be processed as SAE. The researcher will follow up the participant until the end of the pregnancy and should evaluate the outcome in the shortest time possible, but no more than 30 days after the end of the pregnancy. The investigator should notify the sponsor of the pregnancy outcome by submitting a pregnancy follow-up report.

B. *SUSAR and other regulatory reporting and monitoring*: Any Suspected Unexpected Serious Adverse Reaction (SUSAR) will be promptly reported.

The sponsor will ensure that all relevant information about a SUSAR that is fatal or life-threatening is notified to the competent authorities and the relevant IRB or IEC (s) within 7 days after the sponsor is aware of it. of such event and that the relevant follow-up information is communicated within an additional 8 days.

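### Objective 6 compares arms on listed reactions and serious events only, the summary table says all AEs, and the serious-event row is not aligned with section 13

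*Combined protocol and SAP*

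**What the plan says.** Section 11.1 opens by sending the reader to a table of dependent variables for objective 6. That matrix has two yes/no rows.

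- **Anticipated.** A closed list: "Local reactions: pain on vaccination site, swelling, lump itching, bruising", and/or systemic reactions, namely fever of at least 38°C and "muscle ache, joint pain, headache, malaise, fatigue, weakness, sweating, shivering".
- **Serious.** Labelled "Serious, Unanticipated (Clinical"), covering death, life-threatening events, hospitalization or its prolongation, incapacity, and a closing item for other unanticipated events with a serious effect on health. The value scored is simply whether the person had a serious adverse event.

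The analysis text for objective 6 plans descriptive statistics and a Z test to "assess the differences in the proportions of adverse events (anticipated and serious) between the HCP" given each vaccine. The summary table of analyses by endpoint, also in 11.1, gives the criterion as "Frequency of AE", with descriptive statistics and a Z test in the safety population, and names no classes.

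Collection is wider. Section 13.1.4 states: "The investigator is responsible for recording all AEs / SAEs observed during the trial", starting at informed consent. Section 13.1.6 asks for events by non-leading questions and puts serious and non-serious events on the same eCRF screen. Section 13.1.7 runs the observation period to the end of the trial, regardless of cause.

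**The concern.** Section 13.1.1 divides adverse events exhaustively into serious and not serious. The objective 6 matrix divides them into listed reactions and serious events, which is not exhaustive. A non-serious rash or a newly found arrhythmia that does not meet a seriousness criterion would be recorded but would belong to neither row.

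This middle class is where an unexpected, non-serious signal would appear. It matters here because assessing adverse events is a stated objective, section 12 says the adjuvanted vaccine is not authorised in Peru, and section 8 cites licensure for persons aged 65 and older while section 10.1 enrols from age 18. Two analysts following different parts of 11.1 could also report different safety tables.

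The second problem is that the serious-event row restates the definition of an SAE instead of citing it, and the restatement differs from section 13.

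**Working it through.** The documents state no adverse event rate and no safety power, so there is no figure to reproduce. The check sets the sections side by side.

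**Step 1: which events are compared by arm?**

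| Event class | Collected (13.1.4, 13.1.6, 13.1.7) | Matrix row (11.1) | Analysis text (11.1) | Summary table (11.1) |
|---|---|---|---|---|
| Listed local or systemic reaction | Yes | Anticipated | Compared | Covered |
| Serious event | Yes | Serious | Compared | Covered |
| Non-serious event off the list | Yes | None | Not named | Covered, if the wording means all AEs |

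The third line is the gap. The matrix and the analysis text agree with each other, and the summary table can be read more widely. Nothing in the documents says which prevails.

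**Step 2: is the serious row the section 13 definition?**

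| Criterion | Section 13 | Matrix row |
|---|---|---|
| Death | 13.1.2 | Yes |
| Life-threatening | 13.1.2 | Yes |
| Hospitalization or prolongation | 13.1.2 | Yes |
| Disability or incapacity | 13.1.2 | Yes |
| Congenital anomaly in offspring | 13.1.2 | Not named |
| "It is a significant medical event", on medical judgement | 13.1.2 | Replaced by an item limited to unanticipated events |
| Miscarriage, stillbirth; "reported birth defects in the baby are always considered SAE" | 13.1.8 | Not named |

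Four of the six criteria in 13.1.2 match. One is missing and one is narrowed. The pregnancy outcomes of 13.1.8 are also absent.

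**Step 3: would a comparison of the missing class be informative?** This is an illustration only. Section 10.4 gives 400 per group as the maximum. Assume the same true proportion p with at least one such event in each arm. The approximate 95% CI half-width for the risk difference is 1.96 × √(2p(1−p)/400).

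- p = 5%: 1.96 × √(2 × 0.05 × 0.95/400) = 1.96 × 0.0154 = 3.0 percentage points
- p = 10%: 1.96 × √(2 × 0.10 × 0.90/400) = 1.96 × 0.0212 = 4.2 points
- p = 20%: 1.96 × √(2 × 0.20 × 0.80/400) = 1.96 × 0.0283 = 5.5 points

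These rates are assumptions. The point does not depend on them.

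**The case against.** The strongest reply is that objective 6 is worded without restriction and that the summary table already plans a Z test on the frequency of AEs. This stands in part. A reader might infer from the matrix and the analysis text that non-serious, off-list events will never be compared, and the documents do not support that: the summary table allows the comparison. But it is a one-line label that defines no variable, counting unit or window, and it conflicts with the two places that do give detail.

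A reader might also infer that the serious events analysed are not the SAEs of section 13, so that the trial's SAE count will differ from the sponsor's. That is too strong as well. Four criteria are shared, the value scored is just a serious adverse event, the analysis text says serious without the further qualifier, and 13.1.6 has each event classed as serious or not by the section 13 definitions. Nor is a listed reaction that becomes serious left without a place. Within the row's list, the word unanticipated qualifies only the last item, so a reaction leading to hospitalization meets the hospitalization criterion. Only the row label suggests otherwise.

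The omitted pregnancy and congenital outcomes are likely to be few. Section 10.1 requires a negative pregnancy test and willingness to use contraception for at least two months, and the study timeline ends at days 180-200. Some medically attended illness is also covered elsewhere, because section 10.13 lists acute respiratory illness and its medical visits and hospitalizations as outcomes.

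What remains is a contradiction about which events are compared, and a serious-event row that is close to section 13 but not aligned with it.

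**Conclusion.** The concern holds as a reconciliation point. As the matrix and the analysis text stand, one whole class of collected safety data, non-serious events outside the listed reactions, has no variable and no arm comparison, while the summary table implies that it may. The serious-event row departs from 13.1.2 and 13.1.8 in its label, in two of the six 13.1.2 criteria, in the pregnancy outcomes, and in having no cross-reference.

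The number of participants affected cannot be stated. For the serious row it is probably small; for the non-serious class it depends on event rates that the documents do not give. The conclusion rests on reading the matrix and the analysis text as they are written. If the summary table was meant to govern, the defect is the undefined variable, and the change needed is the same.

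**What to change.** In section 11.1:

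1. Add a third variable to the objective 6 matrix, *any non-serious AE outside the listed reactions*. Report participants with at least one such event after vaccination, by vaccine received, with risk difference and 95% CI, as a descriptive comparison.
2. Rename the second row *Serious (any event meeting 13.1.2 or 13.1.8, anticipated or not)* and replace its list of criteria by that reference.
3. Change the parenthesis in the objective 6 text to name all three classes, and word the summary table to match.

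Sub-rows for adverse events of special interest or medically attended events are optional. The visible text mentions the former without listing them, and 13.1.6 does not name medical attendance as an attribute to record. Add them only if they are defined and captured.

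The cost is wording and a few more safety rows, to be read without multiplicity claims. The events themselves are already to be entered in the eCRF.

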7. OBJECTIVE

Primary objective:

-To determine if AD influenza vaccine generates superior immunogenicity than the non-adjuvanted SD influenza vaccine, at approximately 28 days after vaccination and at the end of season, among HCP

Secondary objectives:

-To compare immune responses post-vaccination, at approximately 28 days after vaccination and at the end of season, among HCP with a history of PCR-confirmed influenza infection during any of the six cohort years (2016 to 2021)

-To compare immune responses post-vaccination, at approximately 28 days after vaccination and at the end of season, among HCP with no history of PCR-confirmed influenza infection during the six cohort years (2016 to 2021), among those with data available for the six cohort years -To examine whether the number of prior influenza vaccination during the preceding 10 years, as documented by medical records, modifies immune responses after receipt of vaccination with AD or SD influenza vaccine, at approximately 28 days after vaccination and at the end of season -To evaluate laboratory-confirmed influenza illness rates in the group receiving AD influenza vaccination compared to the group receiving SD influenza vaccination

-To analyze and identify risk factors for sub-optimal response (lack of seroconversion/seroprotection) to SD and/or AD influenza vaccines

- To assess the adverse events among HCP receiving SD and AD influenza vaccines

the studies in reference are those entitled: "Effectiveness of influenza vaccine to prevent infection by influenza virus, loss of hours of work and patient exposure: A prospective cohort study in health workers " that was carried out during the years 2016 to 2019 and "Effectiveness of the influenza vaccine to prevent infection by the influenza virus, loss of working hours and patient exposure: A prospective cohort study in health workers in the context of the COVID-19 pandemic "that was carried out between 2020-2021. Both studies were observational epidemiological studies in hospitals in Lima .

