Primary objective: To determine if AD influenza vaccine generates superior immunogenicity than the nonadjuvanted SD influenza vaccine, at approximately 28 days after vaccination and at the end of season, among HCP. We will use Wilcoxon signed-rank tests to assess HI GMT differences and differences in proportions of HCP who seroconverted and were seroprotected between AD and SD vaccination groups. All HCP included in the clinical trial will be included as the study population for these analyses.

Secondary objectives:

1) To compare immune responses post-vaccination, at approximately 28 days after vaccination and at the end of season, among HCP with a history of PCR-confirmed influenza infection during any of the six cohort years (2016 to 2021). The outcome variables will be the same as those of the primary objective matrix of variables, but dividing the enrolled study population to include only the HCP with a history of PCR-confirmed influenza infection during any of the six-year cohort (2016-2021). We will use Wilcoxon signed-rank tests to assess HI GMT differences and differences in proportions of HCP who seroconverted and were seroprotected between AD and SD vaccination groups. Only HCP in the clinical trial with a history of PCR-confirmed influenza infection during any of the six cohort years (2016 to 2021) will be included as the study population for these analyses.

2) To compare immune responses post-vaccination, at approximately 28 days after vaccination and at the end of season, among HCP with no history of PCR-confirmed influenza infection during the six cohort years (2016 to 2021), among those with data available for the six cohort years. The outcome variables will be the same as those of the matrix of variables in the primary objective, but dividing the enrolled study population to include only the HCP with no history of PCR-confirmed influenza infection during any of the six-year cohort (2016-2021). We will use Wilcoxon signed-rank tests to assess HI GMT differences and differences in proportions of HCP who seroconverted and were seroprotected between AD and SD vaccination groups. Only HCP in the clinical trial with no history of PCR-confirmed influenza infection during any of the six cohort years (2016 to 2021) will be included as the study population for these analyses.

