- ITTm2 population: HCPs who, having been vaccinated, did not become ill with influenza after receiving the AD or SD vaccine at approximately 28 days after vaccination and at the end of the season.
- Safety population: HCPs that were vaccinated with the investigational product

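### Secondary objectives 1 and 2 concern influenza history in 2016–2021, but the populations assigned to them (ITTm1, ITTm2) are defined by influenza illness after the trial vaccine

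*Combined protocol and SAP*

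**What the plan says.** Section 7 sets secondary objective 1 "among HCP with a history of PCR-confirmed influenza infection during any of the six cohort years (2016 to 2021". Objective 2 is the counterpart without such a history, limited to HCP "among those with data available for the six cohort years".

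The analysis text in section 11.1 is introduced as indicating the study population for each analysis. For objective 1 its closing sentence begins "Only HCP in the clinical trial with a history of PCR-confirmed influenza infection during any of the six cohort years (2016 to 2021"; for objective 2 it begins "Only HCP in the clinical trial with no history of PCR-confirmed influenza infection during any of the six cohort years (2016 to 2021".

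The summary table at the end of section 11.1 repeats this. The objective cell of one row reads "among the HCP with a history of influenza infection confirmed by PCR result during any of the 6 years during the previous cohort study" and that of the next "among the HCP who did not have a history of influenza infection confirmed by PCR result during any of the 6 years". The valuation-criteria cells of both rows also speak of history. The population cells of these rows are ITTm1 and ITTm2.

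The list under the table then gives "ITTm1 population: HCPs may, having been vaccinated, became ill with influenza after receiving the AD or SD vaccine" and "ITTm2 population: HCPs who, having been vaccinated, did not become ill with influenza after receiving the AD or SD vaccine". Both definitions end by naming the day-28 and end-of-season time points. ITTm, the parent set, is described as those who did and those who did not fall ill with influenza after the trial vaccine.

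**The concern.** History in 2016–2021 is a baseline characteristic, fixed before anyone is randomised. Influenza after the trial vaccine is a post-randomisation event, and section 11.1 makes it the outcome of secondary objective 5, compared between AD and SD. A programmer who builds analysis sets from the population labels would use the list and obtain the second kind of group.

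Three consequences would follow. Randomisation would no longer protect the AD-versus-SD comparison within each group, because the assigned vaccine may affect who falls ill. End-of-season titres in ITTm1 would mix the antibody response to infection with the response to vaccine. And the comparison that objectives 1 and 2 ask for, AD against SD by prior infection, would not be made. Objective 4 does not replace it: there a previous laboratory-confirmed influenza diagnosis is one of several risk factors for sub-optimal response, not a group within which the arms are compared.

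**Working it through.** The plan gives no figure to reproduce here; the check is a comparison of texts.

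**Step 1. The statements side by side.**

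| Place | Objective 1 group | Objective 2 group | Six-year-data limit (objective 2) |
|---|---|---|---|
| Section 7 | PCR-confirmed influenza, 2016–2021 | none, 2016–2021 | stated |
| Section 11.1, underlined objective | same | same | stated |
| Section 11.1, closing population sentence | same | same | absent |
| Summary table, objective cell | same | same | stated |
| Summary table, valuation-criteria cell | history, years not named | no history, years not named | absent |
| Definitions of ITTm1, ITTm2 | ill with influenza after AD or SD | not ill with influenza after AD or SD | absent |

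Only the last line uses illness after the trial vaccine. Neither definition mentions the cohort, its years or PCR. This is not a garbled fragment: ITTm is written as the union of the same two illness groups, so all three definitions rest on one basis.

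**Step 2. Do the two rules select the same people?** Cross cohort history with illness after the trial vaccine:

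| Cohort history | Ill after trial vaccine | Not ill after trial vaccine |
|---|---|---|
| At least one PCR-confirmed infection | objective 1 / ITTm1: agree | objective 1 / ITTm2: opposite |
| None, data for all six years | objective 2 / ITTm1: opposite | objective 2 / ITTm2: agree |
| None recorded, incomplete data | neither / ITTm1 | neither / ITTm2 |

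For example, an HCP with influenza in 2018 and none after trial vaccination is in objective 1 by history and in ITTm2 by the list. The bottom row can occur: section 10.1 requires participation in the cohort between 2016 and 2021, not in every year. The cells are kinds of participant, not shares of participants. The table shows that the rules differ, not by how much. It also takes a single illness status per person; step 3 considers the alternative.

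**Step 3. Timing.** The closing phrase of the two definitions can be read in two ways.

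- One status per person over the whole season. The day-28 comparison would then depend partly on illness that occurs after the day-28 sample.
- A separate status at each time point. The day-28 comparison would then use illness up to about day 28 only.

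On either reading the group is formed after randomisation and is not the history group.

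**Step 4. Extent.** The summary table has 1 primary + 5 secondary efficacy + 1 safety = 7 rows. The rows for objectives 1 and 2 carry the conflicting labels: 2 of 7 rows, or 2 of the 6 secondary objectives. The primary row is assigned the per-protocol population, which the list defines as all vaccinated HCP without reference to illness.

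**The case against.** The strongest reply is that the intended populations are recoverable. The analysis text announces that it will give the population for each analysis, and its sentences for objectives 1 and 2 are exclusive. Section 7 and the table's own objective and criteria cells agree with them; only the label definitions dissent. This stands. A reader might infer that the plan leaves the choice between the two rules wholly open. The documents do not support that: there is no formal precedence clause, but the weight of the text is on history. The harm described is therefore conditional on someone applying the labels over the text.

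A reader might also infer that the day-28 comparison would necessarily depend on later illness. That holds only under the first reading in step 3, and the documents do not settle which reading is meant.

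The missing six-year-data limit in the closing sentence for objective 2 is largely editorial, since the same paragraph opens with it. Its absence from ITTm2 matters more, because the list is where an analysis set would be looked up.

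Finally, correcting only ITTm1 and ITTm2 would leave ITTm described by post-vaccination illness. That is fair, and the fix below covers it.

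**Conclusion.** The contradiction is real and should be corrected, most probably as a drafting error. As written, the population definitions for secondary objectives 1 and 2 do not match the objectives that they serve, and applying them would give a comparison that randomisation does not protect, in the wrong people.

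The extent is two secondary objectives. A reader might take the cells in step 2 as a measure of misclassification, or suppose a bias towards one vaccine. Neither is supported: the documents give no influenza attack rate for the trial season and no prevalence of prior PCR-confirmed influenza, so no size or direction of bias can be stated. Nor does the point reach the primary analysis. The conclusion rests on the wording alone and needs no assumption about rates; only the day-28 consequence depends on how the closing phrase is read.

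**What to change.** In the list under the summary table in section 11.1:

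- define ITTm1 as vaccinated HCP with at least one PCR-confirmed influenza infection in the 2016–2021 cohort;
- define ITTm2 as vaccinated HCP with data for all six cohort years and no PCR-confirmed infection in them;
- state that both are fixed from cohort records made before randomisation, and that HCP with no recorded infection and incomplete cohort data fall in neither group;
- reword ITTm as all vaccinated HCP. Its membership does not change, since those who fell ill and those who did not together make up everyone vaccinated.

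In the analysis text, repeat the six-year-data limit in the closing population sentence for objective 2.

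The cost is three definitions, one clarifying statement and one sentence. No new data are needed: cohort participation is an inclusion criterion (section 10.1), and the consent covers linkage to the previous study's data (section 10.4). The change should be made before unblinding, so that the populations cannot appear to have been chosen after results were seen.
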